5.1 Primary, Secondary, and Exploratory Endpoints

5.1.1 Primary Endpoint

Greatest change from pre-treatment headache pain intensity to post treatment at any time point within 30 minutes of Nasal CO₂ administration.

5.1.2 Secondary Endpoints

- Percentage of subjects experiencing headache pain freedom at 5-60 minutes within the treated attack
- Percentage of subjects with headache relief at 5-60 minutes within the treated attack
- Rescue medication usage
- Subject satisfaction
- Cluster recurrence

Exploratory endpoints include but not limited to:

- Number of doses per treated attack
- Consistency of response with repeated treated attacks

All primary, secondary, and exploratory efficacy endpoints will be analyzed for the all headaches analyses as well.

5.2 Study Treatment

5.2.1 Dose Description

This is an open-label study so all eligible subjects will receive a nasal CO₂ hand-held dispenser. One dose will consist of a 10 second administration of nasal CO₂ to each nostril. Subjects will be instructed to use the nasal CO₂ dispenser, 10 sec/nostril, as needed up to 6 times to treat one attack. Each dose must be separated by 3-5 minutes. Subjects should treat only one attack during a 24-hour period with the investigational product. Subjects may treat up to three cluster headache attacks during the treatment phase of this study.

Subjects may receive up to a total of 1.0 L of CO₂ if they treat one attack with 6 doses. Subjects may receive a total of 3.0 L of CO₂ if they treat three headache attacks with 6 doses of CO₂ during this study.

5.2.1.1 Nasal CO₂ Dispensers

The dispensers are calibrated to deliver CO₂ at a target flow rate of 0.5 standard liters per minute (SLPM).

5.2.2 Packaging and Labeling

Treatment kits will consist of one (1) dispenser and the Directions for Use. The directions will specify that the dispensers cannot be taken aboard an airplane. There will be replacement dispensers available in the event subjects damage or misplace their dispensers. When subjects are enrolled, they will be assigned a unique subject identification number and a unique kit number.

Once eligibility is confirmed, the study site personnel will review the Directions for Use with the subjects and will give the copy of the Directions for Use to the subjects to take with them.

5.2.3 Storage and Handling

The dispenser should be stored at room temperature (59 – 86 °F / 15 – 30 °C). Prolonged exposure to temperatures above or below ambient conditions should be avoided.

The contents of the dispenser are under pressure. Therefore, exposure of the dispenser to temperatures ≥ 120 °F (50 °C), puncture, or other damage to the dispenser may cause injury and/or loss of contents.

At this time, the Transportation Security Administration (TSA) does not allow the dispenser to be carried aboard any commercial aircraft. If the dispenser is carried through TSA security or onto any commercial flight, it will be confiscated.

Neither the dispenser nor its packaging is child-resistant. It has not been tested in children for safety. Therefore, the dispenser should be kept out of the reach of children.

The dispenser is an investigational drug product and must be stored, handled, and administered in accordance with this protocol, the Investigator's Brochure and labeling, as well as all applicable laws, regulations, and institution requirements.

5.3 Duration

Once enrolled, each subject's participation in the trial may last up to 84 days (12 weeks) or once the subject treats up to 3 cluster headache attacks with the nasal CO₂ dispenser, whichever occurs first. There will be two scheduled clinic visits, Screening and End of Study Visit. The subject may return to the clinic 4 weeks and 8 weeks after the screening visit as necessary for a replacement dispenser. The End of Study Visit should occur within 7 days after the subject treats his/her last cluster headache attack or within 7 days after the completion of the 84-day treatment period, whichever occurs first. If a subject has not treated any cluster headaches during the 12 weeks treatment phase they can be allowed to continue in the study for an additional 12 weeks at the discretion of the Investigator.

5.4 Discontinuation

Based on trials conducted with nasal CO₂ to date, it is not expected that serious safety issues will arise that would require a discontinuation of the study. If such issues do arise, the sponsor, [name], will, in consultation with the Capnia, appropriate regulatory authority(ies), and/or IRB, take the steps necessary to modify or discontinue the trial.

Since this is an open-label, pilot study, there will be an ongoing review of the data. The trial may also be discontinued or modified in the event that the study treatment is not showing any signs of efficacy.

The criteria for the discontinuation of the participation of individual subjects are explained in Section 6.3.

5.5 Investigational Product Accountability

The Investigator, or a responsible party designated by the Investigator, must maintain an inventory record to document the receipt and dispensation of each nasal CO₂ dispenser. All used and unused investigational product will be returned to Capnia or designee. Investigational product will not be dispensed to any person who is not a qualified study subject under this protocol. The investigational product will be dispensed only by study site personnel designated by the Investigator in writing on the Study Site Personnel Signature Log. The investigational product must be dispensed only within and from the institution listed in the study contract and Form FDA 1572. The maintenance of study-related investigational product accountability records does not preclude the Investigator's responsibilities to maintain additional records in accordance with all national and/or local institutional requirements for investigational medication.

Subjects are required to return the used and/or unused dispensers to the study site at the End of Study Visit. Upon completion or termination of the study or on request, all used and unused investigational product will be accounted for and returned to Capnia or designee.

5.6 Data Identification

Clinical data will be directly entered into the combined eSource/CRF forms by members of the study site personnel. Site personnel will be responsible for instructing subjects on the requirement for timely and daily completion of the electronic diary (eDiary). Subject-reported adverse events and concomitant medications collected during the out-subject treatment period will be recorded by the subject in the eDiary. This diary will be reviewed by the Investigator and/or the appropriate study site personnel, applicable information will be collected, recorded into the subject's eSource/eCRF. The electronic diaries will be automatically collected after the completion of each diary and stored with the subject's eSource/CRF documents. Subjects will record their headache-related symptom assessments as well as the details regarding the nasal CO₂ administration in an electronic diary.

6.0 SELECTION AND WITHDRAWAL OF SUBJECTS

6.1 Inclusion Criteria

Subjects must meet all of the following inclusion criteria to be considered eligible for study entry:

- Male or female, 18 years of age and older.
- History of cluster headache, as defined by International Classification of Headache Disorders (ICHD), third edition, beta version guidelines (ICHD-3 beta, Cephalgia 2013).
- Stable on concomitant medications, excluding those for the treatment of cluster headache, for at least 60 days prior to enrollment.

Note: Subjects are allowed to use their usual standard of care for the preventative treatment for their cluster headache. Acute/abortive medications maybe used 60 or more minutes after the initial dose, limited to the following: triptans; high-flow oxygen.

- If female and of childbearing potential, have a negative urine pregnancy test at the time of Screening.
 - To not be considered childbearing potential a subject must be surgically sterile, have had a hysterectomy or tubal ligation, post-menopausal for at least 1 year, or otherwise incapable of pregnancy.
- Capable of completing online headache diary with access to internet.
- Able to provide written Informed Consent.

6.2 Exclusion Criteria

Subjects must not meet any of the following exclusion criteria to be considered eligible for study entry:

- Recent nasal/midface trauma (< 3 months).
- Recent nasal/sinus surgery (< 3 months).
- Severe respiratory distress in the last 6 months.
- Neoplasm such as Angiofibroma, sinus tumor, granuloma.

Protocol 15-001CA
Nasal CO₂

- Nasal congestion present more than 10 days with fever (temperature ≥ 100.4 °F) and nasal mucous is an abnormal color.
- Surgery to treat cluster headache.
- History of aneurysm, intracranial hemorrhage, brain tumors or significant head trauma.
- Structural intracranial or cervical vascular lesions that may potentially cause headache attacks.
- Other significant pain problem (including cancer pain, fibromyalgia and trigeminal neuralgia) which in the opinion of the clinician, may interfere with the study.
- Psychiatric disorder which in the opinion of the Investigator may interfere with the study.
- Pregnant, actively trying to become pregnant, or breastfeeding, and/or is unwilling to use an accepted form of birth control.
 - Acceptable forms include: complete abstinence from intercourse from 2 weeks prior to administration of study drug, throughout the study, and for 7 days after completion or premature discontinuation from the study; sterilization of male partner when in a monogamous relationship; intrauterine device or implant with published data showing lowest expected failure rate is less than 1% per year; double barrier method (i.e., 2 physical barriers OR 1 physical barrier plus spermicide) for a least 1 month prior to Screening Visit and throughout study; or hormonal contraceptives for at least 3 months prior to Screening Visit and throughout study.
- Skin around and inside the nasal passage that is dry, cracked, oozing, or bleeding.
- Recurrent nose bleeds which in the opinion of the Investigator, may interfere with the study.
- Is participating in any other therapeutic clinical investigation or has participated in a clinical trial and received treatment in the preceding 30 days

6.3 Subject Withdrawal

Subjects are free to withdraw consent and discontinue participation in the study at any time without prejudice to further treatment. A subject's participation in the study may be discontinued at any time at the discretion of the Investigator. Justifiable reasons for the removal of a subject from the study include but are not limited to:

- The subject's request
- The subject is non-compliant in the opinion of the Investigator
- The subject resumes or initiates other medication not permitted in this study
- The subject experiences an adverse event which, regardless of seriousness or severity, prohibits further participation in the study
- The subject does not have a cluster headache episode within 84 days (12 weeks) after Enrollment
- The subject becomes pregnant, at which time she is to inform the study site personnel

Enrolled subjects who withdraw from the study must return to the study site for the End of Study Visit. If during this visit, the Investigator determines that the subject has an ongoing study drug-related or study device-related adverse event, the subject will be followed until resolution or stabilization.

The reasons for withdrawal must be documented accordingly in the subject's eSource documents/eCRF. Subjects who withdraw early from the study may be replaced.

6.4 Screen Failures

Subjects who do not meet the eligibility criteria at the Screening Visit will be considered screen failures. These subjects will be instructed by the study site, if the Investigator is the subject's doctor, how to manage their cluster headaches (i.e., continue to use the medication they were previously taking for their cluster headaches prior to being screened for this study) or be referred to their regular physician for management of their cluster headaches. These subjects will not be required to undergo the End of Study Visit procedures.

7.0 TREATMENT OF SUBJECTS

Below is a brief description of the treatments to be administered in this study. Please refer to Section 5.5 Trial Treatment and the Investigator's Brochure for more information regarding nasal CO₂.

7.1 Treatments to be Administered

7.1.1 Nasal CO₂ Dispenser

The subject will administer the nasal CO₂ to one nostril and then to the second nostril (i.e., 10 seconds to the right nostril then 10 seconds to the left nostril). The administrations should

occur in succession and there should be no more than one (1) minute delay between administration each nostril. One dose consists of a 10-second administration of CO₂ to each nostril. If subjects still have pain and/or any other symptoms after the initial dose then they may take up to 5 doses after the initial dose. Each dose must be separated by 3-5 minutes. Thus, subjects may take up to 6 doses of study drug to treat an attack.

If the subject is feeling congested at the time of the study drug administration, he/she may blow his/her nose prior to each dose. The subject will be informed to hold his/her breath or to breathe in and out of his/her mouth during the administration, whichever is more comfortable to the individual subject.

Subjects will treat up to 3 cluster headache attacks within a 84-day period (12 weeks) of their Screening Visit (i.e., when they were enrolled into the study). Subjects will return to the clinic 4 weeks and 8 weeks after the Screening Visit for a replacement dispenser, as necessary.

7.2 Medication

7.2.1 Concomitant Medication

Concomitant medications required by subjects must be documented on their eSource/CRF documents. Patients must be stable on concomitant medications, excluding those for the treatment of cluster headache, for at least 60 days prior to enrollment

Subjects are allowed to take their prescription migraine and cluster prophylaxis medication.

7.2.2 Medications Not Permitted

The investigator or designee will instruct the subjects **NOT** to treat a cluster headache with the study drug if, within 12 hours prior to the onset of the attack, they used any of the following:

- Non-steroidal anti-inflammatory drugs (NSAIDS)
- Non-prescription analgesics
- Narcotic analgesics
- Triptans
- Ergotamine medication or derivatives

- Any other medications or treatments for headache (e.g., homeopathy, natural health products, acupuncture, etc.)

7.2.3 Rescue Medication

Subjects will be allowed to take rescue medication as prescribed by their physician if the headache(s) does/do not resolve or worsen(s) after completing the one-hour assessment. Subjects who take rescue medication will be asked to record the details of all medication taken through the 24-hour assessment (e.g., what medication they took, dose, when they took it, etc.) in the eDiary. The data recorded by the subjects in the diaries will be discussed at the End of Study Visit and all rescue medication taken by the subjects will be recorded on the subjects' appropriate eSource/eCRFs. If a subject uses rescue medication they are not allowed to treat the same headache again with Investigational Product.

Subjects who take rescue medication shall record the severity of their headache and associated symptoms at the 1 hour assessment.

7.3 Monitoring for Subject Compliance

Subjects return to the site approximately 4 weeks after enrollment to exchange study drug and determine the subjects' compliance with nasal CO₂ administration and eDiary completion. If necessary, at these visits subjects can receive re-training if it is determined there are issues with study drug administration and/or diary completion.

8.0 STUDY PROCEDURES

The following sections describe the procedures and assessments that will be performed during the study. The Schedule of Events, located in Section 8.2, indicates the frequency of these procedures and assessments.

8.1 Description of Study Procedures and Assessments

8.1.1 Informed Consent

At the beginning of the Screening Visit, potential participants will be given an IRB-approved informed consent form by a member of the study site personnel (i.e., study coordinator, Investigator, or other study site personnel). Potential participants will be provided time to read the consent form as well as the opportunity to ask questions and have their questions answered prior to the initiation of any study-specific assessments. Subjects must voluntarily provide written informed consent before any study-related assessments are performed. Once signed by the subject and the study site personnel performing the consent process, a copy of the consent form will be given to the subject and the original will be stored in the study site's files. The

subject's medical records/source documents must include documentation that written informed consent was obtained from the subject, and that the subject received copies of the signed, fully-executed informed consent form.

8.1.2 Medical History, Medications and Demographics

Subjects will be asked about their medical history and any medication and supplements they are currently taking or have taken within 30 days of the Screening Visit. Subjects will also be asked about their cluster headache history (e.g., age of diagnosis, typical associated symptoms, cluster headache pattern, etc.) and the pharmacotherapy and/or alternative treatment (e.g., homeopathy, natural health products, etc.) they have taken for their cluster headaches. In addition, the subject's demographic information (age, gender, race, and ethnicity) will be collected.

8.1.3 Physical Examination

A full physical exam, including all major body systems and neurological exam, will be performed at the Screening Visit and at the End of Study Visit. Any conditions or symptoms reported after the subject is enrolled will be recorded as an AE on the AE eCRF. This includes new events after nasal CO₂ administration, conditions that become more severe or increase in frequency, any disease-related signs or symptoms present at the Screening Visit (see Section 8.1.2) that have worsened in severity or frequency, as well as any event or finding that the Investigator feels is clinically significant.

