5.0 TRIAL DESIGN

This is an open-label, investigator-sponsored, pilot study. Subjects agreeing to participate in the study and meeting the eligibility criteria assessed at the screening visit will be enrolled in the study. The length of time between screening and treatment will last between 0 days to a maximum of 12 weeks. Subjects who enter the screening phase during a cluster headache episode and meet the study eligibility criteria can immediately enter the treatment phase and may opt to treat their cluster headache episode in the clinic. Subjects who are not in a cluster

Protocol 15-001CA
Nasal CO₂

headache episode, who meet initial screening eligibility criteria, can remain in the screening phase for up to 12 weeks until their next cluster episode begins. Upon initiation of a cluster headache episode, subjects will enter the treatment period.

Subjects will be trained and demonstrate the proper use of the hand-held dispenser containing CO₂ calibrated to deliver 0.5 standard liters per minute (SLPM). This dispenser will be provided to subjects for use in the clinic or home. Subjects will be instructed to use the nasal CO₂ dispenser, 10 sec/nostril, as needed up to 6 times to treat one attack. Each dose must be separated by 3-5 minutes. Subjects should treat only one attack in a 24-hour period. Subjects may treat up to three cluster headache attacks during the treatment phase of this study. One hour after the first dose subjects can choose to treat with investigator-approved rescue medication. Subjects will be asked to complete an online diary after the completion of the dosing. Diary assessments will collect pain severity (0=none, 1=mild, 2=moderate, 3=severe), symptoms (such as tearing, nasal congestion, and running nose), nasal CO₂ usage, acute medication usage, satisfaction of treatment, number of cluster attacks, and unusual symptoms. Subjects will be contacted by phone within 3 days of the first use of the nasal CO₂ dispenser to assess adverse events (AEs) and medication usage. A total of 25 subjects will enter the treatment period and be instructed to treat up to three cluster headaches with nasal CO₂. Within 7 days of treating their last cluster headache episode, subjects will return for an end of study visit.

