8.1.11 Adverse Events

Subjects will be monitored for safety from the time they are enrolled until the End of Study Visit.

Non-serious adverse events (NSAEs) will be collected beginning after the first dose of study medication through the End of Study Visit and will include any change from the subject's condition at Screening.

SAEs will be collected following enrollment and will include any change from the subject's baseline condition at Screening. SAE collection will conclude at End of Study or until resolution of the SAE if it extends beyond the End of Study Visit.

Subjects will be instructed to record in the eDiary any adverse events they experience from the time they are enrolled at the Screening Visit until their End of Study Visit. Any conditions or symptoms reported will be recorded as an AE in the subject's AE eCRF page. Subjects who have an ongoing AE related to study drug and/or study device will be followed until resolution or stabilization of the event.

At the End of Study Visit, subjects will be asked by the Investigator or an appropriate member of the study site personnel about any AEs they have experienced since the previous visit. All AEs recorded by the subject in the eDiary will be discussed and reviewed by the Investigator or an appropriate member of the study site personnel, recorded in the subject's source documents, and on the appropriate eCRF. Subjects will be instructed to contact the study site in the event they experience any significant AEs. At the discretion of the Investigator, the subject may be asked to come to the study site for an Unscheduled Visit. Additional information regarding AEs is provided in Section 9.0.

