9.2.1 Adverse Event

An adverse event (AE) is any untoward medical occurrence in a subject, or clinical investigation subject, administered a pharmaceutical product which does not necessarily have to have a causal relationship with this treatment. An AE can therefore be any unfavorable and unintended sign (including an abnormal laboratory finding, for example), symptom, or increase in severity or frequency of a pre-existing abnormality, temporally associated with the use of a medicinal (investigational) product, whether or not considered related to the medicinal (investigational) product.

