10.8.1 Adverse Events

Adverse events (AEs) will be monitored throughout the study. All reported AEs will be documented on the appropriate eCRF. All similar AEs will be combined into one category and the frequency of all AEs occurring above 5% will be reported.

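### The adverse-event collection windows contradict each other and 10.8.1 has no split by onset, so background events from a wait of up to 12 weeks can enter the reported AE frequencies

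*Combined protocol and SAP*

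**What the plan says.** The protocol gives two rules for when AE recording starts.

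- **From enrolment.** Section 8.1.3: "Any conditions or symptoms reported after the subject is enrolled will be recorded as an AE on the AE eCRF". Section 8.1.11 opens with "Subjects will be monitored for safety from the time they are enrolled until the End of Study Visit". Its eDiary paragraph has subjects record "any adverse events they experience from the time they are enrolled at the Screening Visit until their End of Study Visit", and then sends whatever is reported to the AE eCRF with no first-dose limit.
- **From first dose, for non-serious events.** Section 8.1.11 also says "Non-serious adverse events (NSAEs) will be collected beginning after the first dose of study medication through the End of Study Visit", and 9.3.1 repeats this. The AE definition in 9.2.1 points the same way, since it speaks of events "temporally associated with the use of a medicinal (investigational) product".

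SAEs are collected from enrolment in both 8.1.11 and 9.3.1. Section 9.1 does not settle the matter, because it refers to 8.1.11, which holds both rules.

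On timing, 5.0 says "The length of time between screening and treatment will last between 0 days to a maximum of 12 weeks", and 7.1.1 places enrolment at the Screening Visit. Section 5.3 allows a further 12 weeks if no attack has been treated, although 6.3 lists the absence of an episode within 84 days as a reason for removal. Training under 8.1.8 includes one activation of 5 seconds per nostril, whereas 5.2.1 defines a dose as 10 seconds per nostril.

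On analysis, 10.8.1 says similar AEs are pooled and "the frequency of all AEs occurring above 5% will be reported". No part of 10.8 defines treatment-emergent events or divides them by onset date. Section 10.8 uses all enrolled subjects; 10.4.4 restricts the safety set to enrolled subjects who received the product at least once.

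**The concern.** Safety is part of the primary objective (4.1), and there is no control group against which background events could be judged. Upper respiratory tract infection, headache and congestion are among the reactions anticipated in 3.4, and all three can plausibly arise without CO₂. If events from the wait are pooled with those after treatment, the AE table partly describes time in which no attack had been dosed. The frequencies would also depend on how many subjects happened to enrol outside an episode, and on which of the two rules each member of site staff applied.

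The procedures can bring such events to light. At the End of Study Visit subjects are asked about AEs since the previous visit, and with only two scheduled clinic visits (5.3) that may be Screening. The telephone calls at about 4 and 8 weeks after Screening (8.1.13) also ask about AEs.

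**Working it through.** The documents give no expected AE rate, so there is no planned figure to reproduce. The check has two parts.

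**1. Which non-serious events from the wait reach the AE form?**

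| Governing rule | Training use counts as first dose? | Non-serious events from the wait |
|---|---|---|
| 8.1.3 and eDiary paragraph of 8.1.11 | either | recorded |
| NSAE sentence of 8.1.11 and 9.3.1 | yes | recorded, because the window opens at Screening |
| NSAE sentence of 8.1.11 and 9.3.1 | no | not recorded; contribution is zero |

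SAEs from the wait are recorded in every row. In the last row, non-serious reactions to the training exposure also go unrecorded. Whatever reaches the form is counted, since 10.8.1 has no onset filter.

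**2. How large could the contribution be?**

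Inputs from the documents: 25 subjects (5.0); a wait of 0 to 84 days; one treated attack per 24 hours, up to three; End of Study within 7 days of the last. Three attacks on consecutive days span 2 days, so the shortest course that uses all three attacks and the full visit window gives 2 + 7 = 9 days.

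Assumptions, not in the documents: 12 of 25 subjects wait 42 days and the other 13 do not wait; follow-up after the first attack dose is 9 days, or alternatively 30; the background rate is 0.5 to 2 AEs per 100 person-days.

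- Person-days in the wait: 12 × 42 = 504.
- Person-days after the first attack dose: 25 × 9 = 225, or 25 × 30 = 750.
- Share of AE time in the wait: 504/(504 + 225) = 69%, or 504/(504 + 750) = 40%.
- Background AEs in the wait: 504 × 0.005 to 504 × 0.02 = 2.5 to 10.1.
- Background AEs afterwards: 225 × 0.005 to 225 × 0.02 = 1.1 to 4.5, or 750 × 0.005 to 750 × 0.02 = 3.75 to 15.

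So the wait contributes more background events than follow-up if follow-up is 9 days, and fewer if it is 30. For a single waiting subject the shares are 42/51 = 82%, 84/93 = 90% (12-week wait), or 42/72 = 58% with 30 days of follow-up. For a subject treated on the day of Screening the share is 0%.

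**The 5% line.** It applies to each AE category. One subject of 25 is 4% and two are 8%, so two are needed. One is enough if the denominator is 19 or fewer (1/19 = 5.3%). With an assumed weekly background rate r for one category, the chance that a subject has the event in a wait of w weeks is p = 1 − (1 − r)^w. The chance of at least two affected subjects is then binomial:

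| r per week | 12 subjects wait 6 weeks: p | chance of ≥2 | All 25 wait 12 weeks: p | chance of ≥2 |
|---|---|---|---|---|
| 0.25% | 1.5% | 1% | 3.0% | 17% |
| 0.5% | 3.0% | 5% | 5.8% | 43% |
| 1% | 5.9% | 15% | 11.4% | 79% |
| 2% | 11.4% | 41% | 21.5% | 98% |

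The right-hand pair is a worst case within the 12-week limit. Both pairs presume that events from the wait are recorded; otherwise the non-serious contribution is zero.

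**The case against.** A reader might infer that events from the wait certainly enter the rates and would be read as CO₂ reactions. The documents do not support that.

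- Section 9.3.1, the dedicated reporting section, begins non-serious collection after the first dose. The Schedule of Events marks AE assessment at Treatment and End of Study, not at Screening. Section 5.0 describes waiting subjects as still in the screening phase.
- Relationship to drug or device is collected for each AE (9.3.1), and suspected adverse reactions are defined separately (9.2.2). Section 10.8.1 promises a frequency of all AEs, not of reactions.
- If training is the first dose, the wait is time after exposure, and counting it is what the after-first-dose rule requires.
- The proportion waiting, the length of the wait and the background rates are all assumed, and 30 days of follow-up reverses the comparison of event counts.
- AE start dates and dose times are already collected, so a split can be made at reporting without loss of data.

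All of this stands, and it limits the point to what can happen rather than what will. It does not resolve the conflict. The schedule does not say which onset dates count, and 9.1 points to a section that contains both rules. The dates make a split possible, but the plan does not call for one.

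**Conclusion.** The point holds as an unreconciled conflict between 8.1.3 with the eDiary paragraph of 8.1.11 on one side, and the NSAE sentence of 8.1.11 with 9.3.1 on the other, combined with an AE summary that ignores onset. Background events from a wait of up to 12 weeks, or longer under the 5.3 extension, can therefore enter the reported frequencies.

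The non-serious contribution lies between zero and, on the assumptions shown, about 2.5 to 10 AEs. SAEs from the wait are included under every reading. The severity is modest: this is an open-label pilot of up to 25 subjects, and no stated decision rests on the 5% line.

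**What to change.** 1. Reconcile 8.1.3 and 8.1.11 with 9.3.1. State one AE start point, and say whether the training use counts as first exposure. Recording from enrolment may stay.
2. In 10.8.1, tabulate AEs by onset in separate columns: before any CO₂ exposure (if any occur); from the training use to the first treated attack; and from the first attack dose to End of Study. The last column takes events that start or worsen in that period, and events dated the same day as the first attack dose count as after it. Reactions to the training use then stay visible without being mixed into the attack-treatment rate.
3. Use as the denominator of each exposure column the subjects exposed in that period; any events before exposure are shown over all enrolled. Subjects trained but never treated then do not dilute the attack-treatment rate. For illustration, 4 affected subjects are 4/20 = 20% if 20 of 25 treated an attack, but 4/25 = 16% over all enrolled. Align 10.8 with 10.4.4 at the same time.

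The cost is a sentence or two in 8.1.3 and 8.1.11, an onset flag derived from dates already collected, and extra columns in one table. The downside is smaller counts per period.
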